10.3.5.2. Clinical Laboratory Assessments (Part A and Part B)

For Part A and Part B of the study, descriptive statistics of actual values and change from baseline for clinical laboratory values (in SI units) will be presented at each assessment timepoint by treatment. In addition, descriptive statistics for values and changes from the baseline values in conventional units at each assessment timepoint will be presented for selected clinical laboratory parameters listed in the SAP.

The criteria for PCS laboratory values will be detailed in the SAP for Part A and the SAP for Part B, respectively. The number and percentage of participants who have PCS postbaseline clinical laboratory values will be tabulated by study treatment at each assessment. The percentages will be calculated relative to the number of participants who have available non-PCS baseline values and at least 1 postbaseline assessment. The numerator will be the total number of participants with available non-PCS baseline values and at least 1 PCS postbaseline value. A supportive listing of participants with PCS postbaseline values will be provided.

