11.2 CLINICAL LABORATORY PARAMETERS

Descriptive statistics for clinical laboratory values (in SI units) and changes from the baseline values at each assessment time point will be presented by treatment group for the following laboratory parameters, measured at Screening and Visit 6/ET:

Hematology: Absolute and differential white blood cell count, erythrocyte count, hemoglobin, hematocrit, platelet count, and red blood cell indices (mean corpuscular volume, mean corpuscular hemoglobin, and mean corpuscular hemoglobin concentration)

Chemistry: Sodium, potassium, calcium, chloride, bicarbonate, magnesium, gamma glutamyl transferase, phosphate, glucose, blood urea nitrogen, creatinine, creatine phosphokinase, total protein, alkaline phosphatase, albumin, bilirubin (total; direct; indirect), ALT, AST, total cholesterol, low-density lipoprotein, high-density lipoprotein, triglycerides

Urinalysis: Specific gravity, pH, protein, glucose, ketones, and blood
Urine drug screen (UDS): Benzoylecgonine (cocaine), barbiturates, amphetamines, benzodiazepines, cannabinoids, opiates, methadone, phencyclidine

Pregnancy at Screening and Visit 6/ET: Serum β -hCG

The following clinical laboratory levels will be measured at Screening only:

Clinical laboratory screening tests: HbA1c, fasting insulin, TSH, T3, and free T4

Hepatitis screening: HCV antibody, hepatitis-B surface antigen, and hepatitis-B core antibody total will be tested. Reflex hepatitis-B core antibody IgM will be performed for all hepatitis-B core antibody total positive or reactive results. Positive test results will be sent for confirmation testing.

Clinical laboratory test values will be considered potentially clinically significant (PCS) if they meet either the lower-limit or higher-limit PCS criteria listed in [Table 11-1](#). The number and percentage of participants who have PCS postbaseline clinical laboratory values will be tabulated by treatment group. The percentages will be calculated relative to the number of participants with available non-PCS baseline values and at least 1 postbaseline assessment. The numerator will be the total number of participants with available non-PCS baseline value and at least one postbaseline assessment. A supportive tabular display of participants with PCS postbaseline values will be provided, including the PID number, baseline and all postbaseline (including non-PCS) values.

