11.3 VITAL SIGNS

Descriptive statistics of actual values and change from baseline for vital signs (systolic and diastolic blood pressures, pulse rate, weight, and temperature) will be presented at each assessment timepoint by treatment.

Vital sign values will be considered PCS if they meet both the observed-value criterion and the change-from-baseline criteria listed in [Table 11-3](#). The number and percentage of participants who have PCS postbaseline vital sign values will be tabulated by treatment group. The percentages will be calculated relative to the number of participants who have available baseline value and at least 1 postbaseline assessment. The numerator will be the total number of participants with available non-PCS baseline value and at least one PCS postbaseline value. A supportive listing of participants with PCS postbaseline values will be provided.

In addition, a tabular display showing all AEs that occurred in participants who had PCS postbaseline vital sign values will be provided.

Table 11-3 Criteria for Potentially Clinically Significant Vital Signs

Parameter	Flag	Criteria ^a	
		Observed Value	Change From Baseline
Supine systolic blood pressure, mm Hg	High	≥ 180	Increase of ≥ 20
	Low	≤ 90	Decrease of ≥ 20
Supine diastolic blood pressure, mm Hg	High	≥ 105	Increase of ≥ 15
	Low	≤ 50	Decrease of ≥ 15
Supine pulse rate, bpm	High	≥ 120	Increase of ≥ 15
	Low	≤ 50	Decrease of ≥ 15
Weight, kg	High	—	Increase of ≥ 7%
	Low	—	Decrease of ≥ 7%
Temperature, °C	High	> 38	—
	Low	< 35	—

a A postbaseline value is considered potentially clinically significant if it meets both the observed-value and the change-from-baseline criteria.

bpm = beats per minute.

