11.4 ELECTROCARDIOGRAM

Descriptive statistics of actual values and change from baseline for ECG parameters (ie, heart rate, PR interval, QRS interval, QT interval, and QTc interval according to QTcB and QTcF) will be presented at each assessment timepoint by treatment group.

Electrocardiographic parameter values are considered PCS if they meet the higher-limit PCS criteria listed in [Table 11-4](#). The number and percentage of participants with PCS postbaseline values will be tabulated by study treatment group. The percentages will be calculated relative to the number of participants with available non-PCS baseline value and at least one postbaseline assessment. The numerator will be the total number of participants with available non-PCS baseline value and at least one PCS postbaseline ECG value. A supportive listing of participants with PCS postbaseline values will be provided and will include the participant number and the baseline and postbaseline values. A listing of all AEs for participants with PCS ECG values will also be provided.

A shift table from Screening to Day 15 in the investigator's overall interpretation of the ECG will be presented by treatment group for the following categories: normal; abnormal, not clinically significant; abnormal, clinically significant. A tabular display of participants with postbaseline clinically significant ECG abnormalities according to the investigator's overall interpretation will be provided.

The number and percentage of participants with a change from baseline QTc > 30 msec but not exceeding 60 msec and of participants with an increase > 60 msec will be tabulated by treatment group. A supportive listing that includes the participant identification number, all QTc values (including change from baseline values), and all AEs will be provided for all participants who have postbaseline QTc changes > 30 msec.

Table 11-4 Criteria for Potentially Clinically Significant Electrocardiograms

Parameter	Unit	Higher Limit
QRS interval	msec	≥ 150
PR interval	msec	≥ 250
QTcB, QTcF	msec	>500 or Change from baseline (increase of > 60)

QTc = QT interval corrected for heart rate.

QTcB = QT interval corrected for heart rate using the Bazett formula.

QTcF = QT interval corrected for heart rate using the Fridericia formula.

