16.3 REPEATED OR UNSCHEDULED ASSESSMENTS OF SAFETY PARAMETERS

If a participant has repeated assessments before the start of the first treatment, the results from the final nonmissing assessment made prior to the start of the study treatment will be used as baseline. If end of double-blind treatment period assessments are repeated or if unscheduled visits occur during the double-blind treatment period, the last nonmissing postbaseline assessment will be used as the end of double-blind treatment period assessment for generating summary statistics. However, all postbaseline assessments will be used for PCS value determinations, and all assessments will be presented in the data listings.

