16.9 CHARACTER VALUES OF CLINICAL LABORATORY PARAMETERS

If the reported value of a clinical laboratory parameter cannot be used in a statistical summary table because, for example, a character string is reported for a parameter of the numeric type, a coded value must be appropriately determined for use in the statistical analyses. The actual values, however, as reported in the database will be presented in the data listings.

[Table 16-3](#) shows examples of how some possible laboratory results should be coded for the analysis.

Table 16-3 Examples of Coding Speci al Character Values for Clinical Laboratory Parameters

Laboratory Test	Possible Laboratory Results (in SI Units)	Coded Value for Analysis
Chemistry: ALT	< 5	5
Chemistry: AST	< 5	5
Chemistry: bilirubin, total	< 2	2
Urinalysis: ketones	> 0	Positive
	≤ 0, Negative	Negative
Urinalysis: pH	> 8.0, ≥ 8.0	8.0
	≥ 8.5	8.5
Urinalysis: glucose	≤ 50	0
	(50, 100]	1+
	(100, 250]	2+
	(250, 500]	3+
	(500, 1000]	4+
	≥ 1000	5+
Urinalysis: protein	≤ 15	0
	(15, 30]	1+
	(30, 100]	2+
	(100, 500]	3+
	≥ 500	4+

ALT = alanine aminotransferase; AST = aspartate aminotransferase; SI = *Le Système International d'Unités* (International System of Units).

17.0

CHANGES TO ANALYSES SPECIFIED IN PROTOCOL

None

18.0 **REFERENCES**

DOCUMENT HISTORY PAGE

Effect Date	Revision Number	Primary Author	Description of Change

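### SAP 11.2 leaves PCS out of the laboratory PCS numerator, so the percentage rule as written gives 100% for every parameter and arm

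*SAP*

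**What the plan says.** SAP 11.2 first states what the table is for: "The number and percentage of participants who have PCS postbaseline clinical laboratory values will be tabulated by treatment group". It then sets the denominator: "The percentages will be calculated relative to the number of participants with available non-PCS baseline values and at least 1 postbaseline assessment". The next sentence sets the numerator: "The numerator will be the total number of participants with available non-PCS baseline value and at least one postbaseline assessment".

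The other places that define the same kind of percentage read differently:

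- Protocol 10.3.5.2, for this laboratory table: "The numerator will be the total number of participants with available non-PCS baseline values and at least 1 PCS postbaseline value".
- SAP 11.3, for vital signs: "The numerator will be the total number of participants with available non-PCS baseline value and at least one PCS postbaseline value".
- SAP 11.4, for ECG: "The numerator will be the total number of participants with available non-PCS baseline value and at least one PCS postbaseline ECG value".

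SAP 17.0, headed "CHANGES TO ANALYSES SPECIFIED IN PROTOCOL", contains only the entry None. SAP 16.3 adds, on repeated and unscheduled assessments: "However, all postbaseline assessments will be used for PCS value determinations, and all assessments will be presented in the data listings".

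SAP 4.0 says that the table, figure and listing specifications are in a separate document, which is not among those reviewed.

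**The concern.** A percentage of participants who become PCS needs a numerator that counts those with a PCS postbaseline value. The SAP 11.2 numerator does not ask for one. It repeats the denominator's conditions, so the percentage cannot vary with the data.

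What is at stake is one descriptive safety table. Among its 33 parameters are ALT and AST, each with a PCS threshold of at least 3 × ULN. Both potential Hy's law definitions in SAP 11.5.2 also require total bilirubin of at least 2 × ULN, so an isolated transaminase elevation does not enter those summaries. In the SAP text, the PCS table is therefore where the by-arm proportion crossing the ALT or AST threshold is reported. Under the rule as written, that proportion carries no information.

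**Working it through.** The documents give no PCS counts or percentages, so there is no planned figure to reproduce. The check compares the definitions and then computes the percentage under each.

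**1. Conditions side by side**

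| Rule | Baseline condition | Postbaseline condition |
|---|---|---|
| SAP 11.2 denominator | non-PCS | at least one assessment |
| SAP 11.2 numerator | non-PCS | at least one assessment |
| Protocol 10.3.5.2 numerator | non-PCS | at least one PCS value |
| SAP 11.3 numerator (vital signs) | non-PCS | at least one PCS value |
| SAP 11.4 numerator (ECG) | non-PCS | at least one PCS value |

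Only the SAP 11.2 numerator lacks the PCS condition.

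**2. Percentage under each rule**

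Let *n* be the number of participants in an arm with a non-PCS baseline and at least one postbaseline assessment, and *k* the number of those with at least one PCS postbaseline value.

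- SAP 11.2 as written: 100 × *n*/*n* = 100% for any *n* ≥ 1, whatever *k* is. For *n* = 0 it is undefined.
- Protocol 10.3.5.2: 100 × *k*/*n*.

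An enumeration of every *n* from 1 to 25 and every *k* from 0 to *n* found no departure from 100% under the SAP wording. For *n* = 25, the planned arm size (SAP 14.0), taken as fully evaluable for illustration:

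| *k* | SAP 11.2 as written | Protocol 10.3.5.2 |
|---|---|---|
| 0 | 100% | 0% |
| 1 | 100% | 4% |
| 2 | 100% | 8% |
| 5 | 100% | 20% |
| 25 | 100% | 100% |

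**3. Scope**

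Table 11-1 lists 10 hematology + 20 chemistry + 3 urinalysis = 33 parameters, tabulated for 4 arms. SAP 11.2 also lists at least 11 parameters with no Table 11-1 criterion, to which the rule does not apply:

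- hematology, 4: erythrocyte count and three red cell indices;
- chemistry, 4: bicarbonate, phosphate, direct and indirect bilirubin;
- urinalysis, 3: specific gravity, pH and ketones.

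**4. Related wording for vital signs (secondary)**

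- Protocol 10.3.5.3 and footnote a of SAP Table 11-3 call a value PCS only if it meets both an observed-value and a change-from-baseline criterion. Table 11-3 gives both for systolic pressure, diastolic pressure and pulse. Weight has only a change criterion and temperature only an observed-value criterion. Read literally, 2 of the 5 parameters (4 of the 10 rows) can never be PCS.
- SAP 11.3 requires a non-PCS baseline in the numerator but only an available baseline in the denominator. For the 4 parameters with a change criterion, a baseline value cannot itself be PCS, so the extra condition removes nobody. It could matter only for temperature, and only if temperature is judged on its observed value alone. Protocol 10.3.5.3 has no non-PCS baseline condition in either part of the fraction.

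**The case against.** The strongest reply is that the 100% comes from reading one sentence in isolation. Two sentences earlier the same paragraph says that the table counts participants with PCS postbaseline values, so SAP 11.2 contradicts itself and does not prescribe 100%. The correct rule stands in Protocol 10.3.5.2. The None in SAP 17.0 suggests that the protocol rule still applies, the parallel rules in SAP 11.3 and 11.4 are right, and no other numerator is plausible. A programmer would probably notice, and the table specifications cannot be seen, so no effect on any output is shown. On vital signs, a dash in Table 11-3 can be read as no criterion required, which leaves the single listed criterion to apply.

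Much of this stands. The intent is clear, this is a slip and not a chosen method, and 100% is what the rule states, not a forecast of the output. The single-criterion reading for weight and temperature is also the natural one.

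It does not remove the point. The numerator sentence is the instruction for computing the percentage, and nothing in the SAP corrects it. SAP 16.3 shows intent but does not supply the missing condition. The literal both-criteria rule for vital signs likewise still conflicts with the single criteria in Table 11-3.

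**Conclusion.** The concern holds. As written, the laboratory PCS percentage in SAP 11.2 is 100% for all 33 Table 11-1 parameters in every arm with at least one evaluable participant. It contradicts its own paragraph and Protocol 10.3.5.2, and SAP 17.0 declares no change.

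Severity is low. The laboratory descriptive statistics, the participant-level PCS display, the adverse event outputs and the Hy's law summaries do not use this numerator, and no efficacy analysis is touched. The correct counts can be rebuilt from the participant-level display.

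The conclusion rests on a literal reading of the rule. No percentage-point error is claimed, because the documents give no PCS counts. It covers Part A only, the part to which this SAP applies. The vital-sign points are secondary wording conflicts: one affects 2 of 5 parameters on a literal reading, and the other has no effect for 4 of 5.

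**What to change.** In SAP 11.2, redefine the numerator as participants with an available non-PCS baseline value and one or more PCS postbaseline values. That restores the Protocol 10.3.5.2 condition and matches SAP 11.4. Check that the separate table specifications carry the same rule.

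For vital signs, state in both Protocol 10.3.5.3 and SAP 11.3 (including footnote a of Table 11-3) how a parameter with only one listed criterion is judged, or change SAP 11.3 alone and record it in SAP 17.0. Use one baseline condition in both parts of the SAP 11.3 fraction. Dropping the non-PCS condition from the numerator would agree with Protocol 10.3.5.3. Adding it to the denominator instead would be a change to declare in SAP 17.0.

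The main correction costs one sentence, and the secondary one a few lines of matching text. Data collection, sample size and efficacy analyses do not change.

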11.3 VITAL SIGNS

Descriptive statistics of actual values and change from baseline for vital signs (systolic and diastolic blood pressures, pulse rate, weight, and temperature) will be presented at each assessment timepoint by treatment.

Vital sign values will be considered PCS if they meet both the observed-value criterion and the change-from-baseline criteria listed in [Table 11-3](#). The number and percentage of participants who have PCS postbaseline vital sign values will be tabulated by treatment group. The percentages will be calculated relative to the number of participants who have available baseline value and at least 1 postbaseline assessment. The numerator will be the total number of participants with available non-PCS baseline value and at least one PCS postbaseline value. A supportive listing of participants with PCS postbaseline values will be provided.

In addition, a tabular display showing all AEs that occurred in participants who had PCS postbaseline vital sign values will be provided.

Table 11-3 Criteria for Potentially Clinically Significant Vital Signs

Parameter	Flag	Criteria ^a	
		Observed Value	Change From Baseline
Supine systolic blood pressure, mm Hg	High	≥ 180	Increase of ≥ 20
	Low	≤ 90	Decrease of ≥ 20
Supine diastolic blood pressure, mm Hg	High	≥ 105	Increase of ≥ 15
	Low	≤ 50	Decrease of ≥ 15
Supine pulse rate, bpm	High	≥ 120	Increase of ≥ 15
	Low	≤ 50	Decrease of ≥ 15
Weight, kg	High	—	Increase of ≥ 7%
	Low	—	Decrease of ≥ 7%
Temperature, °C	High	> 38	—
	Low	< 35	—

a A postbaseline value is considered potentially clinically significant if it meets both the observed-value and the change-from-baseline criteria.

bpm = beats per minute.

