10.3.5.3. Vital Signs (Part A and Part B)

For Part A and Part B of the study, descriptive statistics of actual values and change from baseline for vital signs (systolic and diastolic BP, pulse rate, weight, and temperature) will be presented at each assessment timepoint by treatment.

Vital sign values will be considered to be PCS if they meet both the observed value criterion and the change from baseline value criterion that will be detailed in the SAP for Part A and the SAP for Part B, respectively. The number and percentage of participants who have PCS postbaseline vital sign values will be tabulated by study treatment for each assessment. The percentages will be calculated relative to the number of participants who have an available baseline value and at least 1 postbaseline assessment. The numerator will be the total number of participants with at least 1 PCS postbaseline value. A supportive listing of participants with PCS postbaseline values will be provided.

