10.3.3.2 Clinical Laboratory Assessments	
The following revisions were made (shown in bold italics):
 
The numerator will be the total number of participants with available non-PCS baseline values and at least 1 PCS postbaseline value.
	
This section was revised as a correction.

Section No. and Name	Description of Change	Brief Rationale
10.3.3.3 Vital Signs	
The following revisions were made (shown in bold italics and strikethroughs):
 
Vital sign values will be considered to be PCS if they meet both the observed value criterion and the change from baseline value criterion, if both criteria are available, or meet either the observed value criterion or the change from baseline value criterion that will be detailed in the SAP. The number and percentage of participants who have PCS postbaseline vital sign values will be tabulated by study treatment for each assessment. The percentages will be calculated relative to the number of participants who have an available baseline or non-PCS baseline (for parameters with only the observed value criterion) values and at least 1 postbaseline assessment.
	This section was revised as a correction.
11 References	
The following reference was added:
 
Hamilton, M. The assessment of anxiety states by rating. British J Medical Psychol 1959;32:50-55.
	This reference was added because it is cited in the protocol for the newly added efficacy parameter of HAM-A.
12.2. Appendix 2: Clinical Laboratory Tests	The timing of the final clinical laboratory tests was changed from Follow-up Visit to Visit 6/ET.	The timing of the final clinical laboratory test was clarified.
12.14 Appendix 14 Hamilton Anxiety Rating Scale	This scale was added as an appendix.	This scale was added to an appendix because the HAM-A is now an efficacy assessment in the study.

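### The SAP's vital-sign PCS rule requires two criteria, but Table 11-3 lists only one each for weight and temperature and does not say how the rule then applies

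*SAP*

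**What the plan says.** The two-part rule appears three times, each time without an exception:

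- SAP 11.3, text: "Vital sign values will be considered PCS if they meet both the observed-value criterion and the change-from-baseline criteria listed in" Table 11-3.
- SAP Table 11-3, footnote a, attached to the Criteria header and so covering every row: "A postbaseline value is considered potentially clinically significant if it meets both the observed-value and the change-from-baseline criteria".
- Protocol 10.3.5.3, for both Parts: "Vital sign values will be considered to be PCS if they meet both the observed value criterion and the change from baseline value criterion", with the thresholds left to each Part's SAP.

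In Table 11-3, supine systolic pressure, diastolic pressure and pulse rate each have both kinds of criterion. Weight has a dash in the observed-value column ("Weight, kg High — Increase of ≥ 7"%, and a matching decrease). Temperature has an observed-value limit ("Temperature, °C High > 38", and below 35) and a dash in the change column.

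Weight and temperature are within the planned analysis: "vital signs (systolic and diastolic blood pressures, pulse rate, weight, and temperature) will be presented at each assessment timepoint by treatment". The flag feeds a by-arm table ("The number and percentage of participants who have PCS postbaseline vital sign values will be tabulated by treatment group"), a supportive listing of participants with PCS values, and a display of the AEs in those participants.

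**The concern.** A rule that needs two conditions cannot be applied as written to a parameter that has only one. The sponsor chose thresholds for weight and temperature, so flags were evidently intended, yet the rule stated above the table and in its footnote gives no route to them.

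At stake is what a reader takes from the PCS table. If the rule is programmed literally, weight and temperature show no PCS participants in any of the four arms whatever was measured, and this would look like a safety finding. If it is programmed the other way, the counts are sensible, but nothing in the plan supports them and two programmers could produce different tables. Weight has some relevance here: protocol section 3 lists decreased body weight among the drug-related findings in dogs at 20 mg/kg/day.

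**Working it through.** The plan gives no figure to reproduce, so the check is logical. The inputs are the 10 flag rows of Table 11-3 (five parameters, high and low). One clearly extreme value per row was tested. The baseline and postbaseline values are illustrative assumptions, not trial data.

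Two rules were applied:

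- **Literal:** flag if an observed-value criterion is listed and met, and a change criterion is listed and met.
- **Listed criteria only:** flag if every criterion that is listed is met, with a dash meaning no condition.

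| Row | Baseline → value | Observed value | Change | Literal | Listed only |
|---|---|---|---|---|---|
| Systolic high | 140 → 185 | ≥ 180: met | +45, ≥ 20: met | flag | flag |
| Systolic low | 120 → 88 | ≤ 90: met | −32, ≥ 20: met | flag | flag |
| Diastolic high | 80 → 108 | ≥ 105: met | +28, ≥ 15: met | flag | flag |
| Diastolic low | 75 → 48 | ≤ 50: met | −27, ≥ 15: met | flag | flag |
| Pulse high | 80 → 125 | ≥ 120: met | +45, ≥ 15: met | flag | flag |
| Pulse low | 70 → 48 | ≤ 50: met | −22, ≥ 15: met | flag | flag |
| Weight high | 80 → 90 kg | none listed | 10/80 = +12.5%, ≥ 7%: met | no flag | flag |
| Weight low | 80 → 70 kg | none listed | 10/80 = −12.5%, ≥ 7%: met | no flag | flag |
| Temperature high | 36.8 → 40 °C | > 38: met | none listed | no flag | flag |
| Temperature low | 36.8 → 34 °C | < 35: met | none listed | no flag | flag |

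Literal rule: 6 of 10 rows can be met, and 0 of the 4 for weight and temperature. Listed criteria only: 10 of 10.

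The neighbouring SAP tables do not have this conflict. Table 11-1 also contains dashes, but a laboratory value is PCS if it crosses either limit, so an empty cell does no harm. Table 11-4 writes an explicit *or* into its QTc row. Only the vital-sign rule joins two conditions with *and* over a table with empty cells.

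**Baseline and denominator.** SAP 11.3 counts in the numerator only participants whose baseline was not PCS, but the denominator needs just an available baseline and a postbaseline assessment. Where a change criterion applies, the two agree: a baseline differs from itself by 0, which fails every change threshold (20, 15 or 7%), so no baseline can be PCS. Once temperature is judged on observed value alone, a baseline above 38 or below 35 °C is itself PCS. That participant would sit in the denominator but could never enter the numerator. In an arm of 25 with one such participant and one new PCS case, the plan's percentage is 1/25 = 4.0%, against 1/24 = 4.2% with matched populations. The effect is small, but it arises as soon as the single-criterion reading is adopted.

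**The case against.** The strongest counter-argument is that a dash means no condition, not a condition that fails. The rule refers to the criteria listed in the table, and where one is listed, meeting that one is a natural reading. Table 11-1 uses the dash in that sense. The non-PCS-baseline requirement in the numerator of SAP 11.3 points the same way, because it does work only for a parameter judged on observed value alone, which here is temperature. The ECG section, SAP 11.4, uses the same baseline requirement, so it may simply have been carried across. The specifications for tables and listings are in a separate document (SAP 4.0) that is not available here and may settle the matter.

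Much of this stands. A reader might infer that the PCS counts for weight and temperature are zero in all four arms by construction. The documents do not support that without qualification, because it holds only on the literal reading. A reader might also infer that fever or marked weight change would vanish from the safety report. That is not supported either:

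- SAP 11.3 still summarises values and changes at each timepoint, and SAP 11.0 includes minimum and maximum.
- SAP 16.3 puts all assessments in the data listings.
- Protocol Appendix 4 makes vital-sign abnormalities that the investigator judges clinically significant reportable as AEs, and SAP 11.1 lists all AEs.

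What does not stand is that the plan needs no edit. Three statements say *both* without exception, and the permissive reading departs from all of them. Protocol Appendix 21 shows fallback wording ("if both criteria are available, or meet either the observed value criterion or the change from baseline value criterion") in its Amendment 1 entry. That is a record of changes, not current text, so it neither supplies the missing rule nor counts as an error.

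**Conclusion.** The stated rule conflicts with its own table for two of the five vital signs (4 of 10 flag rows). The PCS results for weight and temperature are either structurally empty or the product of an undocumented programming choice, and the documents do not say which. This rests on the current SAP and protocol text alone and would change if the separate output specifications define the dash. How many flags would be lost on the literal reading cannot be estimated, because the documents give no expected rate of weight change or abnormal temperature.

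The consequence is confined to the by-arm PCS table, its listing and the linked AE display. No efficacy analysis or hypothesis test is affected. The point should be corrected because it is cheap and prevents a misleading row of zeros, not because safety signals would otherwise be lost.

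**What to change.** In SAP 11.3 and Table 11-3 footnote a, replace the two-part rule with: *PCS if the value meets both criteria where both are listed, or the single listed criterion where only one is listed (weight: change; temperature: observed value).*

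For temperature, restrict the denominator to participants with a non-PCS baseline and at least one postbaseline assessment, to match the numerator already specified.

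SAP 17.0 currently reports no changes from the protocol. Record both points there as differences from protocol 10.3.5.3. A protocol amendment is not needed for this alone.

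The cost is one sentence in two places, a short denominator statement, an entry in SAP 17.0 and small changes to the PCS program. No new data are needed.

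### The SAP's vital-sign PCS numerator carries a baseline restriction that its own denominator and the protocol lack; as defined, it can lower only the temperature rate

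*SAP*

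**What the plan says.** SAP 11.3 builds the percentage in two consecutive sentences. The denominator is set "relative to the number of participants who have available baseline value and at least 1 postbaseline assessment". The numerator sentence then reads: "The numerator will be the total number of participants with available non-PCS baseline value and at least one PCS postbaseline value".

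Protocol 10.3.5.3 has the same denominator, "The percentages will be calculated relative to the number of participants who have an available baseline value and at least 1 postbaseline assessment", but its numerator has no baseline condition: "The numerator will be the total number of participants with at least 1 PCS postbaseline value". SAP 17.0, which lists changes to the protocol's analyses, says there are none.

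On what counts as PCS, the SAP text says: "Vital sign values will be considered PCS if they meet both the observed-value criterion and the change-from-baseline criteria listed in" Table 11-3. The table's footnote ties the definition to values after baseline: "A postbaseline value is considered potentially clinically significant if it meets both the observed-value and the change-from-baseline criteria". In the table, supine systolic pressure, diastolic pressure and pulse have both kinds of criterion, weight has only a change criterion, and temperature has only an observed-value criterion (above 38 or below 35 °C).

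**The concern.** The two halves of the percentage describe different groups. A participant with a PCS baseline would stay in the denominator but could never be counted in the numerator, so the rule can only leave a rate unchanged or lower it. It also departs from the protocol without saying so. The ECG rule in SAP 11.4 shows a matched form, with the non-PCS baseline condition in both numerator and denominator; SAP 11.3 has that type of numerator over a different denominator.

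The second problem is definition. PCS is defined for postbaseline values through a change from baseline, and the SAP never says what a PCS or non-PCS baseline is. Two programmers could read the sentence differently and produce different tables from the same data. At stake is whether the vital-sign PCS table can be reproduced and agrees with the protocol.

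**Working it through.** The documents give no PCS rate, so there is no figure to reproduce. Two checks were made.

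**1. Can a baseline value be PCS under Table 11-3?** SAP 11.0 defines baseline as the last nonmissing assessment before the first dose, so the change from baseline at baseline is 0.

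| Parameter | Observed-value limit | Change required | Can a baseline be PCS? |
|---|---|---|---|
| Supine systolic pressure | ≥ 180 or ≤ 90 mm Hg | ≥ 20 mm Hg | No: 0 < 20 |
| Supine diastolic pressure | ≥ 105 or ≤ 50 mm Hg | ≥ 15 mm Hg | No: 0 < 15 |
| Supine pulse | ≥ 120 or ≤ 50 bpm | ≥ 15 bpm | No: 0 < 15 |
| Weight | none | ≥ 7% | No: 0 < 7 |
| Temperature | > 38 or < 35 °C | none | Yes |

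The temperature row assumes that an absent criterion counts as met. The SAP does not say so, but otherwise no temperature could ever be PCS. For the other four parameters the clause removes nobody, and the SAP rate equals the protocol rate.

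**2. Size for temperature.** Let n be participants with a baseline and a postbaseline value, b those with a PCS baseline, x those among b who also have a PCS postbaseline value, and y those with a non-PCS baseline and a PCS postbaseline value. Then:

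- SAP rule: y/n
- Protocol rule: (x + y)/n
- Matched rule (both parts restricted to a non-PCS baseline): y/(n − b)

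Take n = 25, from the planned arm size in SAP 14.0. The values of b, x and y are assumptions, because the documents give no counts.

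| y | b | x | SAP | Protocol | Matched |
|---|---|---|---|---|---|
| 2 | 0 | 0 | 2/25 = 8.00% | 2/25 = 8.00% | 2/25 = 8.00% |
| 2 | 1 | 0 | 2/25 = 8.00% | 2/25 = 8.00% | 2/24 = 8.33% |
| 2 | 1 | 1 | 2/25 = 8.00% | 3/25 = 12.00% | 2/24 = 8.33% |
| 2 | 2 | 2 | 2/25 = 8.00% | 4/25 = 16.00% | 2/23 = 8.70% |

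Against the protocol the shortfall is x/n, or 1/25 = 4.0 percentage points for each participant who is PCS at both times. Against a matched denominator with b = 1, the gap is 4.17 − 4.00 = 0.17 points for y = 1 and 12.50 − 12.00 = 0.50 points for y = 3. With b = 0 there is no difference on any rule.

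**The case against.** The strongest reply is that the clause does nothing for most of the table. The SAP and protocol both require both criteria, a baseline has no change from itself, and so four of the five vital signs give the protocol's rate exactly. That stands. Temperature is affected only if someone has a baseline above 38 or below 35 °C, and nothing in the documents suggests how often that would occur.

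A reader might infer more: that blood pressure and pulse rates are biased downward, and that this matters because the protocol's Introduction reports transient blood pressure lowering in dogs. The documents do not support that. It requires a non-PCS baseline to mean a baseline within the observed-value limit, which the SAP does not say. Even on that reading, a lost case would need a further move in the same direction from an already extreme value: for example, systolic pressure from 90 or below to 70 or below, or pulse from 50 or below to 35 or below. Entry criteria narrow the field too. Exclusion 20 bars a supine heart rate of 45 or below or 120 or above at Screening or Visit 2, and exclusion 21 bars symptomatic or clinically significant blood pressure.

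It is also fair to say that nothing is hidden. SAP 11.3 provides descriptive statistics by timepoint, a listing of participants with PCS postbaseline values and a display of their adverse events, with no baseline restriction on these. SAP 16.3 uses all postbaseline assessments to determine PCS values.

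These replies limit the size of the problem. They do not reconcile the two sentences with each other or with the protocol, and they do not supply the missing definition. Nor does the protocol's history suggest that the clause was meant to remain: Appendix 21 records that Amendment 1 removed non-PCS baseline wording from the vital-sign denominator as a correction.

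**Conclusion.** SAP 11.3 is wrong as written: its numerator and denominator do not match, the numerator contradicts protocol 10.3.5.3, and the departure is not declared in SAP 17.0. Under the two-criterion definition, blood pressure, pulse and weight rates are unaffected. The temperature rate can be understated, never overstated, by 4 points against the protocol rule per participant who is PCS at both baseline and postbaseline in an arm of 25.

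This rests on treating temperature as PCS on its observed-value limit alone and on about 25 evaluable participants per arm. If nobody has a PCS baseline temperature, the numerical effect is zero. What remains is the undefined term, which could lead a programmer to exclude participants already beyond a blood pressure or pulse limit at baseline. Severity is minor: the table is descriptive and no efficacy analysis depends on it.

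**What to change.** Delete the non-PCS baseline condition from the SAP 11.3 numerator, so that it counts every participant with at least one PCS postbaseline value, as protocol 10.3.5.3 does. The denominator can stay as it is. This restores agreement with the protocol and removes the undefined term.

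If the sponsor wants the restriction for temperature, apply it to both numerator and denominator for that parameter only, define a PCS baseline there as a value beyond the observed-value limit, and record the change in SAP 17.0. In either case, add a line stating that a parameter with a single criterion in Table 11-3 is judged on that criterion alone.

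The cost is one or two SAP sentences, with no change to data collection.
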